Funder	
Collaboration for Leadership in Applied Health Research and Care - West Midlands University of Warwick Office [name]

ClinicalTrials.gov Number	
ClinicalTrials.gov Identifier: NCT03637036

Design	
Randomized Controlled Trial. Participants randomized in equal proportions, stratified by site and job role

Participants	
University Hospitals Birmingham NHS Foundation Trust staff eligible for the seasonal influenza vaccination

Sample size	
Up to 18,000

Treatment duration	
About 2-min

Project duration	
5 months October 2018 to February 2019

Short Title: An improvement project around staffs' influenza vaccine uptake

Gantt Chart.

Responsibility of:

University of Birmingham (UofB)	University of Warwick (UofW)	UofW and UHB
---------------------------------	------------------------------	--------------

Stage 1		Sep	Oct	Nov	Dec	Jan	Feb	Mar
Randomize participants to receive different letter types	UHB's Clinical Business Development Lead will create and send a data file to UHB's statistician that identifies each front line staff member, their worksite, and their job role.							
	UHB's statistician will randomize staff (stratified by worksite and job role) to groups that receive different letter types.							
Disseminate letters	UHB's communications team will disseminate the reminders according to the randomization schedule.							
	UHB Occupational Health Department will monitor vaccine uptake as per reporting protocols already in place.							
Retrieve data	UHB's Clinical Business Development Lead will create a data file to send UHB's statistician that describes: (1) the date each participant was vaccinated or no date – up to the 4 th of January, (2) whether each participant indicated refusal to vaccinate, (3) whether each participant indicated receiving the vaccination elsewhere, and each participant's (4) group-assignment, (5) gender, (6) site, (7) job role.							
Analyze data	UHB's statistician will analyze the data.							
Write-up results	UHB's statistician and UofW's researchers will discuss the analyses interpret the findings.							
Write-up full reports	UofW's researchers will write-up the project for publication.							

Short Title: An improvement project around staffs' influenza vaccine uptake

Approvals being sought to conduct this study.

The decision as to whether the present study requires NHS-REC approval was decided using the Health Research Authority's tools: "Is my study research?"¹ and "Do I need NHS-REC approval?"² The outcomes provided by these tools are described in Table 1.

Table 1.

Is my study reseach?	Yes
Do I need NHS-REC approval?	No but may need other approvals, e.g., HRA and potentially site approvals.

Summary of study. (limit 300 words)

Seasonal vaccination against influenza is recommended for NHS staff.^{3,4} To increase vaccination rates, NHS England put forth a Commissioning for Quality and Innovation goal for the 2018/2019 season of 75%.⁵ University Hospitals Birmingham NHS Foundation Trust (UHB) wants its vaccination rate to surpass this target. Since staff get infected outside of the hospital and from patients staff vaccination does not provide significant 'herd immunity'

To reach past targets, every September UHB already invites staff to take up the vaccination, and regularly reminds staff that have not yet vaccinated to do so. The current protocol describes a randomized controlled trial (RCT) in which staff will be sent a different letter when first invited to receive vaccination, and we will compare the proportion of staff that go on to vaccinate after receiving each type of letter..

To conduct the RCT the research team will design four letter styles. One factor will emphasize an authority figure inviting staff to vaccinate (the Chief Executive, who is also a doctor). The other factor will emphasize a competitive social norm describing vaccination rates in peer hospitals, including Addenbrooke's, Cambridge University Hospitals (which has exemplary rates) see appendix A and across American hospitals (which also have high rates). Letters will be sent to staff in the last week in September by UHB's communications team and they will be disseminated in a randomized fashion.

The UoW's role in this study is to advise the study's design and write-up the project for publication. UHB will approve the reminders, send the reminders, retrieve the data, and analyse the data. No individual-level data will be transferred across organizations. All individual-level data will be managed by authorized UHB employees, e.g., a UHB statistician will randomize staff to receive different reminders and analyze the data, and UHB's communication team to disseminate the reminders.

Questions.

Primary: Will the content of different wording on the letters requesting NHS staff to receive the seasonal influenza vaccination affect the rate at which those staff are vaccinated?

Secondary: Will the effect sizes vary across different demographics?

Data/Outcomes.

- Staff IDs- this is needed to randomize and send letters-Will be deleted after data collection ceases
- Staff Name-this is needed to address letters, e.g., “Dear [name]” -Will be deleted after data collection ceases
- Group Number (e.g., 0=letter version one, 1=letter version two, 2=)
- Date of Vaccination at Trust (DD-MM-YYYY, or blank if the vaccination was never received),
- Indicating Refusal to take up the vaccination (0=No, 1=Yes),
- Indicating Vaccinating at non-Trust Location, e.g., general practice (0=No, 1=Yes)

There are no secondary outcome measures, but information related to the participants’ worksite, job role and gender will be used as predictors in the secondary analyses.

- Worksite (0=Queen Elizabeth, 1=Heartlands, 2=Solihull, 3=Good Hope),
- Job role (1=Doctor, 2=Nurse, 3=Other-frontline), 4=Other-non-frontline),
- Gender (0=Female, 1=Male, 2=Not indicated).

Data retrieval will be facilitated by UHB’s Clinical Business Development Lead from UHB's MyFluJab database, and from Occupational Health data systems.

Analyses.

The primary analysis will compare the proportions of staff that take up the vaccination in each group, where each group receives a different letter. The rates of vaccination will be analyzed with a binary logistic regression model including an interaction term and the two main effects. While all forms of wording will encourage uptake, we hypothesise that some will work better than others.

The secondary analysis will look for differences in the letter wording effectiveness related to sub-group demographics, i.e., worksite, job roles, and gender.

Analyses will be conducted by a UHB statistician according to UHB’s secure protocols.

Short Title: An improvement project around staffs' influenza vaccine uptake

Summary of main issues.

No significant ethical, legal, or management issues arise from this study.

The largest risk of this study is the opportunity for NHS staff data to be leaked. To minimize this risk, no individual-level data will be transferred across organizations. Rather all data will be retrieved and analyzed by authorized UHB staff.

Scientific Justification.

This research is worth doing because current vaccination rates among NHS staff remain lower than desired. The variation among NHS trusts' vaccination rates (from less than 40% to more than 80%)⁶ suggests that some trusts' may doing something better. Unfortunately, reviews of past data do not easily indicate malleable factors as to why the rates differ. The current study will examine one malleable factor that may affect uptake rates, i.e., the content of letters asking staff to vaccinate.

Design and methodology.

Null Hypothesis: All the letters will similarly influence the rate at which staff take up the vaccination.

Alt Hypothesis: The letters will differently influence the rate at which staff take up the vaccination.

The RCT method was selected, because it is the most robust method through which to make causal inferences. The RCT method is feasible, because UHB already monitors whether each staff member receives the vaccination.

There will be no 'no-treatment' control group. All letters will non-coercively invite NHS staff to take up the vaccination, though we expect some reminders to work better than others.

Letter wordings are given Appendix A. One factor will emphasize an authority figure inviting staff to vaccinate. The other factor will emphasize a competitive social norm describing peer hospital performance. Letters will be sent both by e-mail and through the internal post.

UHB's Clinical Business Development Lead will send UHB's statistician a data file in mid-September containing information about staff who should be invited to have a vaccination:

- (1) IDs-needed to randomize at an individual level
- (2) Staff Name-needed to address reminders, e.g., "Dear [name]"
- (3) Worksites-needed to stratify randomization, and
- (4) Job Roles-needed to stratify randomization.

We expect this file to include up to 18,000 NHS staff members, and this number is more than sufficient for our primary comparison. UHB's statistician will randomize these staff to receive one of the letters and then will help UHB's communications team to disseminate the letters according to the randomized schedule.

In January UHB's Clinical Business Development Lead will send UHB's statistician a data file describing whether those staff randomized to receive a letter went on to get vaccinated by the 4th of January. The data will contain information describing each staff member's:

- (1) ID,
- (2) Worksite,
- (3) Job Role,
- (4) Gender,
- (5) Group,
- (6) Date vaccination was received at Trust, if ever,

Version 2.0

7 September 2018.

of 15

Short Title: An improvement project around staffs' influenza vaccine uptake

- (7) Whether the staff member indicated not intending to take up vaccination, and
- (8) Whether the staff member has indicated receiving the vaccination from another source, e.g., general practice.

UHB's statistician will analyze the data and then interpret the findings with UoW's researchers. UoW's researchers will write-up the findings for publication.

Randomization Process.

Yes.

Each NHS staff member will be randomized to one of the available groups, and each group will receive a different letter.

The randomization will be stratified by worksite and job role. The random number function RAND in Microsoft Excel will be used to generate random numbers and within each of the 12 strata the 25% of staff with the lowest values will be assigned to group 1, etc.

Participants.

Samples Size: Up to 18,000

How was the sample size decided? UHB aims to vaccinate approximately 18,000 NHS staff. The following sample-size calculations were performed (using an assumed alpha rate of 0.05 and a beta of 0.8) for a binary logistic regression model including an interaction term as well as two main effects.

To detect an interaction such that the uptake is 40% in three of the groups and 50% in the other group will require a sample-size of at least 750 per group. Thus, we have a sufficient sample size to find a much smaller difference overall and differences in sub-groups.

[figure not shown]
Inclusion: All UHB staff eligible for the seasonal influenza vaccination are eligible for this study.

Exclusion: No patients will be excluded.

Duration in study: NHS staff will be monitored in this study for approximately 4 months, i.e., from the date the letter is disseminated (near the end of September) through the 4th of January 2019. Note that our observations only involve recording when NHS staff receive the vaccination, and such data are already routinely recorded.

Risks: There are no risks beyond standard practice. The largest risk regards NHS staff's personal data being leaked. To minimize the risk of data leaks, no data will be transferred across organizations. Rather data will be retrieved and analyzed by authorized UHB staff according to UHB's standard protocols.

Benefits: NHS staff participants will contribute to our understanding of what types of reminders more effectively motivate NHS staff to vaccinate.

Participant Identification/Recruitment.

How will potential participants, records or samples be identified? Who will carry this out and what resources will be used?

UHB's Clinical Business Development Lead will identify NHS staff members who should be vaccinated using regularly collected information in UHB's Information Systems.

We will be using the IT Flu Application developed in-house by UHB's Information Technology team from which UHB can extract staff level data indicating who has been vaccinated and their role. We will use similar systems at the other sites

Will the identification of potential participants involve reviewing or screening the identifiable personal information of patients, service users or any other person?

Yes.

The identification of potential NHS staff members will involve reviewing the identifiable personal information.

UHB's Clinical Business Development Lead will identify NHS staff members who are eligible to be vaccinated using regularly collected information in UHB's Information Systems.

Describe what measures will be taken to ensure there is no breach of any duty of confidentiality owed to patients, service users or any other person in the process of identifying potential participants.

To minimize the risk of data leaks, no data will be transferred across organizations. Rather data will be retrieved and analyzed by authorized UHB staff according to UHB's standard protocols.

Will researchers or individuals other than the direct care team have access to identifiable personal information of any potential participants?

No

Will any participants be recruited by publicity through posters, leaflets, adverts or websites?

No

How and by whom will potential participants first be approached?

NHS staff participants will not be explicitly recruited, because their part in this study will be incidental as part of their normal staff experience. Recall that UHB already reminds staff to receive the vaccination and monitors whether those staff are vaccinated.

Will you obtain informed consent from or on behalf of research participants?

No.

As stated above (for the How and by whom question), participants' part in this study will be incidental.

Will you recruit any participants who are involved in current research or have recently been involved in any research prior to recruitment?

Not known.

No steps will be taken to find out whether the NHS staff are involved in other research, because (regardless of their involvement in other research) all staff are regularly reminded to

take up the seasonal influenza vaccination.

Will you be undertaking any of the following activities at any stage (including in the identification of potential participants)?

Participants in this study are NHS Staff. The data collected are already regularly gathered and analyzed by UHB administrators for reporting.

Information about the data storage.

Please describe the physical security arrangements for storage of personal data during the study?

The data will be encrypted during transfer between authorized UHB staff over UHB network connections. No data will transfer outside of UHB.

The data will be stored by UBS's statistician during the study in password protected files according to UHB's standard protocols.

How will you ensure the confidentiality of personal data?

No personal data will be stored after the data retrieval has ceased. Rather all personal data will be deleted and replaced with an anonymous ID.

Who will have access to participants' personal data during the study?

Only authorized UHB will have access to that data during the study.

Where will the data generated by the study be analyzed and by whom?

The data files used during this study will be created by UHB's Clinical Business Development Lead at UHB according to UHB's standard protocols.

The data will be analyzed by a UHB statistician according to UHB's standard protocols.

Who will have control of and act as the custodian for the data generated by the study?

The data custodian will be a UHB statistician named in this protocol. If this UHB statistician is not able to fulfill this duty, an amendment will be submitted to replace the named statistician. The UHB statistician will conduct all analyses and no data will be transferred outside UHB.

For how long will you store research data generated by the study?

10-years

How long will personal data be stored or accessed after the study has ended?

No personal data will be stored after the study ends.

Please give details of the long term arrangements for storage of research data after the study has ended.

No identifiable data will be stored after data collection has ceased.

The non-identifiable data will be stored on secure UHB servers in a password protected file. The statistician named on this protocol will have access to the data and will allow access to the data to regulators if requested.

Will you inform participants of the results?

The findings will be shared through the UHB's regular communication channels, e.g., the Trust's newsletter and all staff briefing.

Funder Responsibility.

CLAHRC money will be made available to cover 2.5% of [name] FTE salary over the duration of this project, i.e., approximately 4 hours per month. CLAHRC money will also be made available to pay for the dissemination materials if necessary, e.g., publication cost.

Conflicts of interest

Neither the participants nor the research team members will receive any payments (beyond typical salary) or other reimbursements for their part in this study.

Study Management.

The Study Management/Steering Committee will meet at the beginning of the study (October) the middle (December) and the end (March) to discuss the study and manage any concerns. Members are as follows:

- [name]
- [name] [name]
- [name]
- [name]
- [name]

Additional people may join the meeting upon as necessary to address issues as they arise.

Dissemination outside of UHB Authorship.

The findings will be written-up for an academic journal and may be presented at conferences/workshops. Any publication/presentation will acknowledge the funder's support.

All protocol contributors will be eligible for authorship. The author order and the addition of authors will be determined by the chief investigator.

Approvals to conduct.

The study described in this protocol will not be initiated before the protocol has received approval/favorable opinion from the Health Research Authority (HRA) and participating sites. If HRA deems that this study requires a sponsor, any consideration for amendments will immediately be given to the sponsor with a detailed justification. The sponsor will then decide whether such amendments constitute a non-substantial or substantial amendments. Amendments that require HRA approval will not be instituted until they received approval/favorable opinion from the HRA. Minor amendments may be implemented immediately, and the HRA will be informed.

The study will be conducted in accordance with the ethical principles that have their origin in the Declaration of Helsinki, 1996,⁷ the principles of Good Clinical Practice,⁸ and the Department of Health Research Governance Framework for Health and Social Care, 2005.⁹

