2. DATA

Data collection is described in protocol (version 2, page 5). However, deviations from the protocol resulted in modifications to some of the data we will have available for the analyses. Table 1 describes the data contained in the data file.

The first deviation occurred because of the four worksites originally planned to be in the trial, three could not take part. This left one worksite in the trial, i.e. Queen Elizabeth Hospital.

The second deviation affects our plans for sub-group analyses. This occurred because the trust records describe job roles differently than stated in the protocol. So instead of the job roles stated in the protocol, staff were stratified by two Employment-Types and four Job-Types.

The third deviation occurred as 898 (10.6%) of the hospital's 8438 staff randomized were allocated to a fifth, no-letter, control group. The remaining 7,540 staff were randomized to the planned four groups in equal numbers (i.e., 1885 participants to each of four groups). We will analyse data in the four groups per the original protocol and this will be the primary analysis. However, we will also carry out a subsidiary analysis to compare the results of this no-letter control group to the letter groups, as described in the below section titled 'Supplementary Analysis'.

Table 1. Data in the project analysis file

Type	Name	Codes
Intervention	Group Number	0 = Standard, 1 = Social Norms, 2 = Authority 3 = Combined, and 4 = No Letter Control
Demographics	Gender	0 = Female, and 1 = Male
	Type of Employment	0 = Bank, and 1 = Substantive
	Job Type	0 = Healthcare assistants and other support staff, 1 = Medical and dental staff, 2 = Nursing, midwifery and health visiting staff, and 3 = Scientific, therapeutic and technical staff (for the analyses, groups 0 and 3 will be combined)
Primary Outcome	Date of vaccination at Trust	DD-MM-YYYY, or blank if the vaccination was never received
Other outcomes (formally self-reported)	Refusal to take up the Vaccination	0 = No, and 1 = Yes
	Vaccinating at a non-trust location	0 = No, and 1 = Yes

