3. ANALYSIS OBJECTIVES

- Objective 1 is to assess the effects of the two intervention types (Social Norms and Authority) and any interaction effect of these interventions on the on-site vaccination rates by the end of the trial, i.e. 4th of January 2019.
- Objective 2 is to assess the effects of the interventions on subgroups of the study. We are most interested in comparisons across the above stated three job types, though we will also compare the effects across genders. We will not examine the type of employment because the bank sub-group is small, but we will report the proportion of staff taking up the vaccine in this subgroup.
- Objective 3 is to assess cumulative rates of vaccinations across each group by week from the beginning to the end of the study period.

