4. GENERAL ANALYSIS CONVENTIONS

All descriptive statistics will be reported with 95% confidence intervals, and statistical analyses will be two-sided.

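### The protocol's claim that the sample suffices for sub-group differences is not met, by its own 750-per-group figure, for the two-letter-factor interaction in at least one job type, and the SAP does not update it

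*Combined protocol and SAP*

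**What the plan says.** The protocol's sample-size paragraph (Participants) works "using an assumed alpha rate of 0.05 and a beta of 0.8" and "for a binary logistic regression model including an interaction term as well as two main effects". The target is an interaction in which "the uptake is 40% in three of the groups and 50% in the other group", and this "will require a sample-size of at least 750 per group". With up to 18,000 staff expected, it concludes: "Thus, we have a sufficient sample size to find a much smaller difference overall and differences in sub-groups".

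The SAP (section 2, Data) reports that three of the four worksites could not take part: "This left one worksite in the trial, i.e. Queen Elizabeth Hospital". Of 8,438 staff randomized, 898 were placed in an unplanned no-letter group. The other 7,540 were split equally, 1,885 to each letter. Two of the four recorded job types are merged for analysis, leaving three.

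On Objective 2 the SAP (section 3) says: "We are most interested in comparisons across the above stated three job types". Section 5 tests six interaction terms, including Social Norms x Authority x Job type, and keeps only those that are significant. The SAP sets employment type aside as a sub-group comparison because the bank group is small. It makes no corresponding statement about the size of the job types and does not return to the sample-size conclusion.

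**The concern.** The sufficiency statement compares 750 with a planned 4,500 per letter. Less than half of that is available, and it is divided among three job types that the SAP treats as its main sub-group question. If the protocol's own minimum is not met within a job type, the statement cannot be carried forward for the interaction it was calculated for.

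What is at stake is how Objective 2 is read. An interaction term that is not significant leaves the model. If the three-way term is more likely than not to be missed at the effect size the protocol chose, its absence says little about whether the letters combine differently across job types. The SAP does not say how an absent term will be interpreted, so the risk is of misreading rather than of a stated wrong conclusion.

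**Working it through.** **Inputs.** Protocol, Participants: alpha 0.05; 80% power (the stated beta of 0.8 is read as power); uptake 40/40/40/50%; 750 per group; up to 18,000 staff. SAP section 2: 8,438 randomized, 898 no letter, 1,885 per letter, three job types after merging. SAP section 4: "statistical analyses will be two-sided". The documents do not give job-type or gender counts.

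**1. Reproduce 750.** Let n be the number per letter group; z = 1.960 + 0.842 = 2.80, z² = 7.849.

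- Risk-difference scale: n = z² × Σp(1−p) / δ² = 7.849 × (3 × 0.24 + 0.25) / 0.10² = 7.849 × 0.97 / 0.01 = 762.
- Logit scale: n = z² × Σ1/[p(1−p)] / (ln 1.5)² = 7.849 × 16.5 / 0.405² = 788.
- Power at n = 750: 79.4% (risk difference), 78.0% (logit).

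One-sided testing gives 600 to 621, 90% power gives 1,019 to 1,055, and power of 20% gives 121 to 126. So 750 is a fair, slightly low figure for 80% power, two-sided.

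**2. Planned and actual numbers per letter.**

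- Planned: 18,000/4 = 4,500. Average per job role: 4,500/4 = 1,125 over the protocol's four roles, or 4,500/3 = 1,500 over three.
- Actual: 7,540/4 = 1,885; 1,885/3 = 628 on average. The smallest job type therefore has at most 628, whatever the split.
- For 750 in all three: 3 × 750 = 2,250 per letter, or 9,000 letter recipients.
- Without the no-letter group: 8,438/4/3 = 703, still below 750. The lost sites are enough to cause the shortfall.

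**3. Power for the 40/40/40/50% interaction within one job type.** Power = Φ(0.10/√(0.97/n) − 1.96) on the risk-difference scale; Φ(0.405/√(16.5/n) − 1.96) on the logit scale.

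| n per letter | Risk difference | Logit |
|---|---|---|
| 750 | 79% | 78% |
| 628 (best case for the smallest type) | 72% | 71% |
| 500 (assumed) | 62% | 61% |
| 400 (assumed) | 53% | 51% |
| 300 (assumed) | 42% | 41% |
| 1,885 (whole trial) | 99% | 99% |

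**4. Detectable interaction, 80% power, 40% baseline:** 2.80 × √(0.97/n) = 4.1 points at 4,500, 6.4 at 1,885, 11.0 at 628.

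**5. Terms that compare job types,** assuming three equal types and the effect in one only. The test has 2 df and noncentrality λ = δ² × w₁w₀/(w₁ + w₀), where w₁ is the inverse variance of the estimate in the affected type and w₀ the sum over the other two.

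- Social Norms x Authority x Job type: w₁ = 628/0.97 = 647, w₀ = 2 × 628/0.96 = 1,308, λ = 0.01 × 433 = 4.33, power 45%. On the logit scale, 43%. At 1,500 per cell, 81–83%.
- One factor x Job type, 10-point effect: each arm pools two letters, so 1,256. w₁ = 1,256/0.49 = 2,563, w₀ = 2 × 1,256/0.48 = 5,233, λ = 17.2, power about 97%. For a 5-point effect, about 44%.

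**6. Gender.** 1,885/2 = 942 on average. A gender falls below 750 only if its share is under 750/1,885 = 39.8%.

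**7. Higher baseline.** Letters two to four in the protocol's appendix cite 71.6% uptake among frontline staff at the one remaining hospital last winter. At baselines of 70% to 71.6%, Σp(1−p) is 0.79 to 0.76. The same 10-point interaction then needs about 597–620 per group (risk difference) or 527–555 (logit), and 1,885 per letter detects about 5.6–5.7 points.

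**The case against.** The strongest reply has four parts.

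*The protocol sentence was sound when written.* It predates randomization and was made for up to 18,000 staff. A reader might infer an arithmetic error in the protocol. There is none: 750 reproduces, and the SAP reports the lost sites and exact group sizes openly. This stands, and it places the gap in the SAP, which was written to deal with further analyses and a deviation.

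*Objective 2 is wider than this interaction.* A reader might infer that all sub-group analysis is now inadequate. The numbers do not support that. Four of the six interaction terms pair one factor with job type or gender, and a 10-point effect of that kind keeps about 97% power with equal job types. A 10-point main effect within a job type needs only about 388 per arm, or 194 per letter. No shortfall is shown for gender. This stands. The point is confined to the Social Norms x Authority interaction within and across job types.

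*The three-way term was never promised 80% power.* With four equal roles of 1,125 and 3 df, the same calculation gives about 68–70%. Also, 1,125 is only an average: any role under 4 × 750/18,000 = 16.7% of staff was already below 750. So the low three-way power is not a property lost with the sites. It is still a reason not to read a non-significant term as evidence of no difference.

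*The 40% baseline may be too low.* At the remaining hospital's previous uptake, 628 could suffice if job types are equal. That is correct, but the protocol chose 40%, the SAP adopts no other baseline, and unequal types could still fall short. It is a reason to state the baseline with any detectable effect.

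Table 2 of the SAP already gives uptake with exact 95% intervals by letter within each job type. That helps the reader, but it gives neither an estimate nor an interval for the interaction.

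**Conclusion.** The point holds in a limited form. By the protocol's own benchmark, at least one of the three job types is too small for the Social Norms x Authority interaction: at most 628 per letter against 750. That bound needs no unpublished counts. Power for the 40/40/40/50% pattern is at most about 71–72% in the smallest type and lower if the types are unequal. For the three-way term it is about 43–45%, assuming equal types and the interaction in one only.

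The half of the statement about a smaller overall difference survives: 99% power for the protocol's pattern, and about 6.4 points detectable at 40% uptake. A reader might infer that the primary analysis is underpowered; it is not, for the effect the protocol specified.

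The power figures rest on the protocol's 40% baseline, two-sided 5% tests and large-sample approximations. This is a gap in a secondary objective that the SAP should close, with no bearing on the primary analysis.

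**What to change.** Amend the SAP, leaving the protocol as the record of what was planned.

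- Section 2 or 3: state that the protocol's sub-group sufficiency statement no longer applies to the Social Norms x Authority interaction within job types.
- Same place: add a small table of the interaction detectable with 80% power, with its baseline. At 1,885 per letter this is about 6.4 points at 40% uptake and about 5.6–5.7 at 70–72%. Give the value for each job type from its actual count.
- Section 5: label the Social Norms x Authority x Job type term exploratory, report it as an estimate with 95% CI whether or not it is significant, and draw no conclusion of no difference from a non-significant result.

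The cost is a sentence and a small table. No more staff are needed and the primary analysis is unchanged. The stated capability becomes less favourable.
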